#### Food Allergy Independent Measure (FAIM)

The FAIM questionnaires capture the subject's expectation of something happening because of her/his food allergy.

Each item of the FAIM is answered on a 7-point scale (0 to 6) and should be recoded 1 to 7.

Total FAIM scores will be calculated by dividing the sum of completed items by the number of completed items. Total FAIM scores range from 1 "low perceived disease severity" to 7 "high perceived disease severity".

Calculation of total FAIM scores will be done only when 80% or more of the items are completed.

Some specific items as mentioned below have to be reversed:

- FAIM-CF: Child Form (8-12 years)  
This questionnaire consists of 6 items. The mean score will be performed if at least 5 items are completed.
  
- FAIM-PF: Parent Form (Children aged 0-12 years)  
There are 2 sections given in the questionnaire each with the same items :
  - one from the perspective of the parents (What chance do you think your child has of.....?)
  - one reflecting the thoughts of the child (What chance does your child think he/she has of.....?).

Both mean scores of the parent's form ("Parent's thoughts" and "Child's thoughts") are calculated as the mean of the single items, only if none of the items is missing. In both scores item 4 needs to be reverse scored.

Baseline and Month 12 values for each item of the FAIM questionnaires will be summarized overall and by treatment group, in the ITT population.

Baseline, Month 12 and change from Baseline of the FAIM questionnaires (global score, scores by domain) will be summarized overall and by treatment group, in the ITT population.

Baseline, Month 12 and change from Baseline of the FAIM questionnaires (total score, as well as values at each item of the questionnaires) will also be summarized using descriptive statistics by response status (Responder/Non responder), in the ITT population.

FAIM data will be listed.

#### 4.9 Study Drug Safety Evaluation

The safety analysis will be run on the safety population, successively on the following set of subjects:

- For all subjects
- For the subjects within the age range 4 to 5 years: 4 to 6 years old (6 years excluded)
- For the subjects within the age range 6 to 8 years: 6 to 9 years old (9 excluded)
- For the subjects within the age range 9 to 11 years: 9 to 12 years old (12 excluded)
- For each ED screening subgroup

Some safety sub-analyses will be also run on subjects with mutations in the filaggrin gene versus subjects carrying the wild type gene.

Results will be presented by treatment group and overall.

Unless specified no missing data will be replaced/imputed (see Section 4.9.1).

Symptoms due to DBPCFC will be reported in specific pages of the eCRF and not in the AE form, unless the reaction is serious. SAEs due to DBPCFC will be presented separately from AEs (see [Section 4.9.10](#)) and will be excluded from all tables and listings summarizing AEs/TEAEs.

#### 4.9.1 Adverse Events

Treatment-emergent AEs will be defined as any AEs, regardless of relationship to study drug reported during or after the initial Viaskin® patch application, i.e.:

- New event, or
- Condition already present that worsens in either severity or relationship to study drug following exposure to Viaskin® patches.

AEs occurring after the end of the study (Visit 11 or Visit 12) will be recorded only if the investigator considers that there is a causal relationship with the study drug and as such, will be considered also as TEAEs.

Pre-treatment emergent AE will be defined as an AE that begins before the first administration of study drug and that does not worsen in severity after the first administration of study drug. During the screening period (from the ICF signature to Day-1), only SAEs are recorded in the database (AEs are only documented in the source documents).

Where dates are missing or partially missing, adverse events will be assumed to be treatment-emergent, unless there is clear evidence (through comparison of partial dates) to suggest that the adverse event started prior to the first dose of study treatment.

More specifically:

- Start date of AE missing: Assumed to be date of first treatment dose.
- Start day and month of AE missing: Assumed to be date of first treatment dose (if same year for both dates), January 1st otherwise.
- Start day of AE missing: Assumed to be date of first treatment dose (if same month and year for both dates), first day of the month otherwise.
- End date for non-ongoing AE missing: Assumed to date of last treatment dose
- End day and month for non-ongoing AE missing: Assumed to be date of last treatment dose (if same year for both dates), December 31st otherwise.

- End day for non-ongoing AE missing: Assumed to be date of last treatment dose (if same month and year for both dates), last day of the month otherwise.

TEAEs with missing severity will be considered as “severe”; TEAEs with missing relationship to the study drug will be considered as “drug-related”.

TEAEs reported as related, probably related, or possibly related to the study drug will be considered as related to IP.

Viaskin Peanut-induced Local TEAEs are defined as TEAEs considered as related to IP with a High Level Term equal to “Application and instillation site reactions” and will be flagged in the analysis datasets.

For each summary presented by SOC and PT, the SOC “General disorders and administration site conditions” will be tabulated globally as well as split in 2 subsections:

- General disorders (High Level Term not equal to “Application and instillation site reactions”),
- Administration site conditions (High Level Term equal to “Application and instillation site reactions”).

All AEs will be coded using the latest available version of the MedDRA dictionary.

Symptoms related to DBPCFC are reported in tables separately from other AEs.

AEs related to accidental peanut consumption are reported with other AEs.

An overall overview table of AEs (to be distinguished from symptoms/reactions elicited during the DBPCFCs) will be provided showing the number of subjects, the percentage of subjects and the number of events, overall and for each treatment group, for the following categories of AEs:

- Any AE,
- Any serious AEs,
- AEs leading to study treatment discontinuation,
- AEs leading to death,
- Any mild AEs,
- Any moderate AEs,
- Any severe AEs.

Additionally, an overall overview table of TEAEs will be provided showing the number of subjects, the percentage of subjects and the number of events for the following categories of TEAEs:

- Any TEAE,
- Any serious TEAEs,
- Any TEAEs considered related to IP:
  - ┆ Any TEAE reported as related,
  - ┆ Any TEAE reported as probably related,
  - ┆ Any TEAE reported as possibly related,
- Any TEAEs considered unrelated to IP:
  - ┆ Any TEAE reported as unlikely related,
  - ┆ Any TEAE reported as unrelated,
- Any Serious TEAEs considered related to investigational product (IP),
- Any TEAEs leading to permanent study treatment discontinuation,
- Any TEAEs leading to temporary study treatment discontinuation,
- Any TEAEs leading to death,

- Any mild TEAEs,
- Any moderate TEAEs,
- Any severe TEAEs,
- Any severe TEAEs considered related to IP (reported as related, probably or possibly related),
- Any Viaskin Peanut-induced Local TEAE,
- Any severe Viaskin Peanut-induced Local TEAE,
- Any systemic allergic TEAE considered related to IP (reported as related, probably or possibly related)
- Any TEAE leading to an epinephrine intake
  - ⌞ Considered related to IP
  - ⌞ Considered unrelated to IP.

For TEAEs, TEAEs considered related, SAEs, serious TEAEs, serious TEAEs considered related, TEAEs leading to permanent study treatment discontinuation, TEAEs leading to temporary study treatment discontinuation, Viaskin Peanut-induced Local TEAEs and TEAEs leading to death, detailed tables will be created showing the number of subjects who experienced at least one TEAE, the corresponding percentage of subjects and the number of events by SOC and PT.

Adverse events will be ordered by decreasing frequency on the total population by SOC and by PT within the SOC.

Additional tables will be created to display the most frequent TEAEs (by preferred term), occurring in at least 5% of the subjects in any of the treatment groups. Most frequent TEAEs will also be determined on sub-populations defined by class of age and the corresponding table will be displayed.

Additionally, tables showing the number and percentage of subjects who experienced at least one TEAE and the number of events by SOC and PT, summarizing TEAEs leading to:

- Epinephrine use:

- Standard medication name that contains “EPINEPHRINE”

- Systemic or inhaled corticosteroid use,

- ATC code starting with “H02”
- ATC code starting with “A07EA”, “C05”, “R01” and (ROUTE in "ORAL" "RECTAL" "RESPIRATORY (INHALATION)") or (ROUTE=OTHER with other, specify that contains ("IV" "INTRAVENOUS"))

- Topical corticosteroid use,

- ATC code starting with “D07”
- ATC code starting with “A07EA”, “C05”, “R01” and ROUTE = Topical

will be presented (exhaustiveness of the above selections, especially regarding the route that can be reported as “Other” with a text field specification, will be checked during the blind data review meeting).

These TEAEs will be identified according to the 2 conditions below:

CCI

CONFIDENTIAL

Project Document Version No. 3.0

Project Document Effective Date: 04-Oct-2017

Page 51 of 79

- In the AE form: TEAEs for which a medication is administered (“Were there any medication administered for this adverse event? answered “Yes”)
- In the Concomitant medication form for the medication considered: corresponding AE numbers documented in the field “Number of adverse events for which the medication was taken”

For TEAEs and TEAEs considered related to IP, additional tables will be provided showing number of subjects and percentage of subjects:

- By maximum severity (severe, moderate and mild): Subjects will be counted once per SOC and once per PT at the worst severity. If the severity is missing, the worst severity will be assumed.
- By maximum duration. For these tables TEAEs will be presented by SOC, PT within each SOC and maximum duration within each PT (using the classes for duration in days: 1-7, 8-15, 16-30, 31-60, 61-90, above 91). For AEs ongoing at the end of the study, duration will be imputed based on the date of subject end of study. For AEs not ongoing but with missing end date, duration will be imputed based on date of last study treatment.

Additionally, for TEAEs and TEAEs considered related to IP, tables showing number of subjects, percentage of subjects and number of events by severity will be provided. Subjects will be counted once per SOC, per PT and per severity. For these specific tables, if the severity is missing, no hypothesis will be assumed to replace the missing severity.

Adverse event summaries will be ordered in terms of decreasing frequency for SOC, and PT within SOC, in the Viaskin® treatment group, and then similarly by decreasing frequency in the placebo group, and then alphabetically for SOC, and PT within SOC.

The proportions of patches during the one-year exposure period that led to mild, moderate or severe TEAE considered related to IP will be summarized on the Safety population (overall, by screening ED subgroup and by class of age). For this analysis, the worst ongoing severity will be considered for each day of exposure and the following definitions will be used:

- % of patches leading to severe TEAE will be estimated as =

$$100 \left( \frac{\text{Number of days with ongoing severe TEAE}}{\text{Exposure duration}} \right)$$

- % of patches leading to moderate TEAE will be estimated as =

$$100 \left( \frac{\text{Number of days with ongoing moderate (1) TEAE}}{\text{Exposure duration}} \right)$$

(1) without concomitant event of severe intensity

- % of patches leading to mild TEAE will be estimated as =

$$100 \left( \frac{\text{Number of days with ongoing mild (2) TEAE}}{\text{Exposure duration}} \right)$$

(2) without concomitant event of moderate or severe intensity

The proportion of patches during the one-year exposure period that led to Viaskin® Peanut 250 µg-induced AEs will also be summarized the same way as above.

A by-subject listing of all adverse events will be provided. This listing will be presented by treatment group and will include: treatment group, subject identifier, age, sex, adverse event (SOC, PT, and verbatim term), date/time of onset (and corresponding study day), date/time of resolution (and corresponding study day), duration, severity, treatment required, relationship to study drug, relationship to an accidental peanut consumption and relationship to DBPCFC, action taken with the study drug, outcome, and whether the event is classified as serious or not with the corresponding criteria.

Pre-treatment emergent adverse events will be listed separately the same way as the treatment emergent adverse events.

TEAE leading to an epinephrine intake will also be listed.

Finally, SAEs will also be listed the same way with an additional flag for treatment emergent SAEs.

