#### 6.2.1.4 Recording Adverse Events

Adverse event reporting will start at the signature of the informed consent form (ICF) and end after the 2-week follow-up period (End of Study V12 Visit). During the screening period (that is, from the time of ICF signature through Day-1), only SAEs will be recorded in the e-CRF; during the screening period, AEs that do not meet any seriousness criteria will be documented in the subject's source documents. Adverse events occurring after the end of the study should be reported to the Sponsor by the Investigator if the Investigator considers that there is a causal relationship with the study drug.

Adverse events still ongoing at the time of the End of Study Visit will be followed up for an additional 30 days, or until they resolve or stabilize, whichever comes first.

All AEs occurring on or after the day of the first dose of study drug, regardless of the relationship to the study drug, will be recorded in the e-CRF.

All AE reports in the e-CRF should contain the following information of the event: date and time of onset, date and time of resolution, severity, treatment required, relationship to study drug, action taken with the study drug, outcome, and whether the event is classified as serious or not.

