#### **7.2.10 Visit 11 ( $\leq 1$ week after Visit 10), End of Treatment Period**

Visit 11 corresponds to the end of the 12-month treatment period. Patch application ends at this visit. The patch worn by the subject when she/he arrives to this visit is removed and there will be no further patches applied beyond Visit 11.

Visit 11 corresponds to the second day of the post-treatment DBPCFC after 12 months of treatment. It takes place within a week following the first day of the post-treatment DBPCFC.

The following assessments will be performed at this visit:

- Physical examination (including a complete skin examination; to take place before DBPCFC; see [Section 6.2.4](#));
- Vital signs (to take place before DBPCFC; see [Section 6.2.3](#));
- PEF (to take place before DBPCFC; see [Section 6.2.6](#));
- Post-treatment DBPCFC (second day) (see [Section 6.1.1](#))
- AEs recording (including volunteered or solicited AEs, AESIs, and recording of AEs/allergies in response to the DBPCFC);
- Concomitant medications (including any medications given to treat allergic symptoms) (see [Section 5.8](#));
- Check for any accidental peanut consumption (see [Section 6.4.4](#));
- Check that the subject diary has been completed accurately and ensure that the subject/parents/guardians is/are comfortable with using the diary;
- Dispense subject diary (re-instruct subjects/parents/guardians on the use, if necessary; see [Section 6.2.7](#));
- Collect the treatment box dispensed at the visit 10 (Month 12 visit), check the unused medication and assess medication compliance;
- Patch adhesion Investigator's assessment: with the patch still applied, the Investigator assesses the adherence of the patch to the skin as well as the occlusion of the patch chamber;
- Check skin reactions of all zones of application and grade the overall severity of the skin reactions (see [Table 6](#), [Section 6.2.8](#));
- Take a photograph of the sites of application of the Viaskin® patch, load it onto the PEPITES website (described in [section 6.2.8](#)) and keep it in the subject's medical records or source documents;
- Schedule Visit 12.

Physical examinations, assessment of vital signs and PEF measurements can be repeated during the DBPCFC as deemed necessary by the Investigator.

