##### **Analyses of other efficacy, safety and exploratory criteria:**

No imputation will be performed for other efficacy, safety and exploratory criteria (observed data will be used). Partial or missing safety data will be imputed according to the most conservative approach. Adverse events with missing or incomplete onset date will be considered as TEAEs unless there is evidence that the event occurred prior to the treatment period. Treatment-emergent AEs with missing relationship to the study drug will be considered as drug-related and TEAEs with missing severity will be considered as severe. Actual values will be presented in listings.

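### SAP 4.9.1 sets a missing adverse-event end date to the last treatment dose with no floor at onset, so an event that starts after the last patch ends before it begins and fits no duration class

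*SAP*

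**What the plan says.** SAP 4.9.1 gives three rules for the end date of an adverse event that is no longer ongoing.

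- End date fully missing: "End date for non-ongoing AE missing: Assumed to date of last treatment dose".
- Day and month missing: the last-dose date if the year matches that of the last dose, otherwise 31 December.
- Day missing: the last-dose date if month and year both match, otherwise the last day of the month.

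The same section repeats the first rule for duration: "For AEs not ongoing but with missing end date, duration will be imputed based on date of last study treatment". Events still ongoing run instead to the child's end of study. Maximum duration is then tabulated for TEAEs and for related TEAEs, "using the classes for duration in days: 1-7, 8-15, 16-30, 31-60, 61-90, above 91".

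On when patches stop and how long events are collected, Protocol 7.2.10 states that "there will be no further patches applied beyond Visit 11", and Protocol 6.2.1.4 states "Adverse event reporting will start at the signature of the informed consent form (ICF) and end after the 2-week follow-up period". Protocol 7.2.12 has adverse events recorded at an early termination visit held after the child stops study drug. SAP 4.9.1 extends collection further: "AEs occurring after the end of the study (Visit 11 or Visit 12) will be recorded only if the investigator considers" them causally linked to study drug, and it counts those events as TEAEs.

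On the general approach, Protocol 8.2.2.4 says: "Partial or missing safety data will be imputed according to the most conservative approach". SAP 4.8.1.2 says the same for safety data and refers to 4.9.1 for the detail.

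**The concern.** The end-date rule assumes that every event begins while the child is still on patches. The plan's own collection window does not. TEAEs are defined from the first patch application onward with no upper limit at the last patch, so off-patch events enter the duration tables. For such an event the rule produces an end before the start.

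A milder version affects events that began on treatment and continued after it. If one is recorded as resolved with no end date, the rule closes it on the day of the last dose. That could matter for a child who stopped because of the event.

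At stake is the maximum-duration table for TEAEs and related TEAEs. Affected events would have no class or would be shortened, and two programmers working independently from the SAP would have to invent a way to handle them.

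**Working it through.** **Inputs.** L is the date of last dose and S = L + k is the onset, k days later. The rule-based end is L (SAP 4.9.1). The SAP gives no formula for adverse-event duration, so both usual conventions are shown.

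**Fully missing end date.**

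- end − start = L − (L + k) = −k
- end − start + 1 = 1 − k

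| k (days after last dose) | end − start | end − start + 1 | Class under end − start + 1 |
|---|---|---|---|
| 0 | 0 | 1 | 1-7 |
| 1 | −1 | 0 | none |
| 2 | −2 | −1 | none |
| 7 | −7 | −6 | none |
| 14 | −14 | −13 | none |

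The reversal occurs for every k ≥ 1. Counting both end days, the duration is 0 at k = 1 and negative from k = 2. The lowest class starts at 1 day, so all of these fall outside the table.

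**Partial end date.** With last dose 10 June, onset 17 June and end recorded only as June of the same year, the month and year match. The end becomes 10 June and the duration is 10 − 17 + 1 = −6 days. If the end month is later than the last-dose month, the rule takes the last day of that month and no reversal occurs. A match on year alone matters only when day and month are both missing.

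**Events that began on treatment.** Let onset be j days before L.

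- True end m days after L: imputed duration j + 1, true duration j + m + 1, so the rule is m days too short.
- True end m days before L: imputed duration j + 1, true duration j − m + 1, so the rule is m days too long.

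As an illustration of the second case, take an assumed onset on Day 60 and last patch on Day 365. The imputed duration is 365 − 60 + 1 = 306 days, in the top class, however soon the event cleared.

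**Conditions for the reversal.** The onset must be known and lie after the last dose, the event must be recorded as resolved, and its end date must be missing or partial as above. A fully missing onset is set to the first dose, so it cannot reverse. In a temporary interruption the last dose usually falls after onset, so the problem belongs to permanent stopping.

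**Is there a guard elsewhere?** SAP 4.7 deals with negative durations, but only for patch wear time. SAP Appendix 5 sets aside events with missing dates, but only when pairing events in the systemic-allergic algorithm. Neither reaches adverse-event duration.

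**Class labels.** The classes run 61-90 and then above 91, so exactly 91 days has no class.

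**The case against.** The strongest reply is that the case is rare and its effect confined. Protocol 6.2.1.4 asks for date and time of resolution on every report, 6.2.1.6 has events followed to resolution, and 9.2.1 and 9.4 provide data checks, queries and plausibility rules. Children who roll over finish at Visit 11, where patches stop, and so have no off-patch follow-up in this study. Incidence, severity, relatedness and efficacy do not use end dates. The percentage-of-patches summaries count days of exposure, so off-patch days do not enter. Actual values go into listings, so the recorded date stays visible. All of this stands. It makes the situation uncommon but does not change what the rule produces when it arises.

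Three stronger readings are tempting, and the documents do not support them.

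- *That the last-dose anchor is the least conservative choice and breaks the plan's commitment.* It shortens only events that outlast the last patch and lengthens those that resolved earlier. In the previous study in children, 241 of 343 related TEAEs (70.26%) arose before Day 180 (Protocol Table 4), so lengthening may well be the commoner error. The examples that Protocol 8.2.2.4 gives of its conservative approach concern onset, relationship and severity, not end date.
- *That about 50 children are affected.* 330 × 0.15 = 49.5 is the planned drop-out, which SAP 4.12 calls a maximum. It does not count events that meet the conditions above.
- *That moving the anchor to the end-of-study date cures the problem.* A related event can start after study end, and the reversal then returns.

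**Conclusion.** The rule is wrong as written: for a class of events that the plan collects and counts as TEAEs, it gives an end date before the start date and a duration that no table row can hold. The result follows from the stated rule and needs no assumption beyond one such event occurring. Whether the first off-patch day gives 0 or −1 depends on the unstated duration formula; either value is unclassifiable.

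The size is small. The documents give no count of affected events, and the conditions are narrow. The effect is limited to adverse-event duration, chiefly the maximum-duration tables. The cut at the last dose for events that outlast it is a real but two-sided imprecision, not an error of the same kind. This is a low-priority correction, worth making because it is so cheap. The 91-day gap is a separate wording slip and adds no weight.

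**What to change.** Add one sentence to SAP 4.9.1: no imputed adverse-event end date, whether fully missing or partial, may precede the onset date, so the imputed end is the later of the rule-based date and onset. Apply the same floor to the end-of-study rule for ongoing events, because a related event can begin after study end. With the floor, every event with k ≥ 1 and a missing end date gets end = start and, counting both end days, a duration of 1 day in the 1-7 class. Events starting on or before the last dose are unchanged.

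State the duration formula at the same time, and relabel the top class as 91 or more.

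For events starting on or before the last dose, moving the anchor to the end-of-study date is optional. It would avoid cutting events that outlast the patch, at the price of lengthening those that resolved earlier still further.

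The cost is a few words in the SAP and a small change to the date derivation.
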